3. EOT assessments are to be performed at premature withdrawal or treatment failure and within 24-h of last dose. If EOT occurs on the same day as a dosing day during hospitalization then the visit should be completed as an EOT visit.
4. A symptom directed Physical Exam should be conducted daily while in hospital. Complete physical exams should be performed at Screening, Day 5, EOI, EOT, TOC and FU visits.
5. Temperature (oral, rectal, tympanic, or by temporal artery) should be assessed per institution guidelines while in hospital, and the highest daily value recorded in the eCRF.
6. RR, HR, B/P at: (i) Screening, (ii) daily while in hospital, (iii) Day 5, (iv) EOI, (v) EOT, (vi) TOC, and (vii) FU.
7. At screening visit, record all prior and concomitant medications, including all prescription, over-the-counter and herbal medications, taken within 1 week prior to randomization, including both day and time for all antibiotics administered in the 72-h prior to randomization. The following subjects who have received previous/ongoing antibiotics are eligible for enrollment: (a) subjects with suspected acute cUTI who have received a single dose of effective non-study antibiotics for the acute cUTI; (b) subjects who developed signs and symptoms of cUTI while on an antibiotic for another indication. No concomitant systemic antibacterials effective in cUTI are permitted after the initial dose of study drug through the FU visit, other than subjects on rescue/non-study antibacterial therapy. See Protocol Section 10.6 for prohibited concomitant medications.
8. Hematology and chemistry will be performed at: Screening, EOI, EOT, TOC, and FU.
9. Urine microscopy for RBC, WBC, crystals, and casts performed at: (i) Screening, (ii) Day 5, (iii) EOI, (iv) EOT, (v) TOC, and (vi) FU.
10. If creatinine clearance is <50 at Screening, creatinine clearance should be recalculated daily through Day 5 and thereafter as clinically indicated. Creatinine clearance should be calculated based upon local laboratory results in order to make timely dose adjustments, if needed; however, samples are also required to be sent to the central lab for assessment. Ertapenem/placebo and levofloxacin dosing should be increased or decreased according to the prescribing information.

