Subjects who receive any systemic concomitant antibiotic therapy from the first dose of study drug through the Day 5 Visit (CE-Day 5 population), EOI Visit (CE-EOI population), EOT Visit (CE-EOT population), TOC Visit (CE-TOC population) and FU Visit (CE-FU population) that is potentially effective against the baseline pathogen will be excluded from the CE populations with the following exceptions:

- The subject is a clinical failure at Day 5 (CE-Day 5 population), EOI (CE-EOI population), EOT (CE-EOT population), TOC (CE-TOC population) or FU (CE-FU population) and received non-study antibiotics for insufficient therapeutic effect of the study drug
- The subject received an oral antibiotic with no systemic absorption

Subjects who do not have a pathogen isolated at baseline and receive an antibiotic with expected activity against cUTI pathogens will also be excluded from the CE populations unless considered a failure by the Investigator at Day 5, EOI, EOT, TOC or FU and received non-study antibiotics for insufficient therapeutic effect of the study drug. Subjects who receive a systemic concomitant antibiotic that is not effective against the baseline pathogen, or if no pathogen is isolated and the antibiotic does not have activity against cUTI pathogens, will be included in the CE populations.

4. Study Drug Therapy:

Subjects must meet all of the following to be included in the CE populations:

- Received the correct study drug based on the randomization assignment for the entire treatment period
- Study personnel involved in the assessment of efficacy or monitoring efficacy data remained blinded to treatment assignment, unless a treatment limiting AE occurred which required unblinding
- The subject received at least 3 days of study drug
- The subject was at least 80% compliant with study drug

5. Clinical Outcome Assessment:

Subjects must meet the following to be included in the CE populations:

- For the CE-Day 5 population:
 - Completed the Investigator's assessment of clinical response (ie, was not deemed an indeterminate outcome) at the Day 5 Visit
 - The Day 5 Visit occurred 4-6 days following randomization
- For the CE-EOI population:
 - Completed the Investigator's assessment of clinical response (ie, was not deemed an indeterminate outcome) at the EOI Visit

- The EOI Visit occurred within 1 day of the last dose of IV study drug
- For the CE-EOT population:

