 - Completed the Investigator's assessment of clinical response (ie, was not deemed an indeterminate outcome) at the EOT Visit
 - The EOT Visit occurred within 1 day of the last dose of study drug (IV or PO)
- For the CE-TOC population:
 - Completed the Investigator's assessment of clinical response (ie, was not deemed an indeterminate outcome) at the TOC Visit, unless the patient was defined as a clinical failure at the EOT Visit
 - The TOC Visit occurred 13-18 days following randomization and at least 5 days following the last dose of study drug, unless the subject was considered to be a clinical failure based on the Investigator's assessment at the EOT Visit
- For the CE-FU population:
 - Completed the Investigator's assessment of clinical response (ie, was not deemed an indeterminate outcome) at the FU Visit, unless the patient was defined as a clinical failure at the EOT or TOC Visits.
 - The FU Visit occurred 20-29 days following randomization, unless the subject was considered to be a clinical failure based on the Investigator's assessment at the EOT or TOC Visits.

6. Baseline or Inter-Current Medical Events:

Subjects will be excluded from the CE populations if the Investigator has documented in the eCRF that they meet any 1 of the following protocol-defined exclusion criteria at baseline (ie, prior to randomization):

- Exclusion criterion 2: History of an ertapenem-resistant urinary tract infections within 1 year of consent
- Exclusion criterion 3: Likely to require > 10 days of antibiotic treatment to cure the acute cUTI or likely to receive ongoing antibacterial drug prophylaxis prior to the FU visit (eg, subjects with vesiculo-ureteral reflux)
- Exclusion criterion 6: Complicated pyelonephritis with complete obstruction or known or suspected renal or perinephric abscess, emphysematous pyelonephritis, OR Any condition likely to require surgery to achieve cure (this does NOT include procedure to place catheters or obtain diagnosis)
- Exclusion 7: Known or suspected fungal infection
- Exclusion 8: Uncomplicated lower urinary tract infection

- Exclusion 9: Suspected or confirmed active prostatitis, or currently under treatment for prostatitis
- Exclusion 10: Subjects with high risk for cUTI due to *Pseudomonas* sp. (eg, History of prior cUTIs due to *Pseudomonas*, ≥ 20 mg QD prednisone or equivalent steroid, and other risk factors as perceived by the investigator)

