3.1.7. Microbiologically Evaluable (ME) Populations

The ME-Day 5, ME-EOI, ME-EOT, ME-TOC and ME-FU populations will consist of all subjects in the micro-ITT and the CE-Day5, CE-EOI, CE-EOT, CE-TOC, CE-FU populations, respectively who also meet the following:

- Had a suitable urine specimen (as defined in [Section 3.1.4](#)) collected at the Day 5 (ME-Day 5), EOI (CE-EOI), EOT (ME-EOT), TOC (ME-TOC) and FU (ME-FU) Visits. Subjects who are microbiological failures prior to the TOC or FU Visit, and are otherwise evaluable, will be included in the ME-TOC and ME-FU populations regardless of when the TOC and FU visits occurred.
- The urine culture at the Day 5 (ME-Day 5), EOI (ME-EOI), EOT (ME-EOT), TOC (ME-TOC) and FU (ME-FU) Visits is interpretable with respect to determining microbiological outcome. An interpretable urine culture is one that has a clearly identified pathogen or one where the baseline pathogen(s) can be excluded. A urine culture will be considered uninterpretable if more than 2 bacterial isolates are identified unless the specimen is obtained via suprapubic aspiration, nephrostomy tube newly placed or cystoscopy, 1 of the isolates comprises $\geq 80\%$ of the total growth (predominant), 1 or more isolates are also isolated simultaneously from a blood culture, or there is $< 10^4$ CFU/mL (including no growth) of the baseline pathogen(s).

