5.7.1. Primary Efficacy Analysis

The primary outcome measure is a responder outcome derived from both clinical response and microbiological response at the EOI and the TOC Visit in the micro-ITT population.

Clinical Response:

Clinical response is based on the Investigator Responses on the CRF and is not derived programatically. Clinical response is classified by the Investigator as cure, failure or indeterminate based on the following definitions:

- **Clinical Cure:** Clinical cure is defined as complete resolution or significant improvement of signs and symptoms of the infection such that no rescue/non-study antibacterial therapy is required to treat the cUTI that presented at study entry

- **Clinical Failure:** Subjects are classified as a clinical failure based on:
 - Death related to cUTI at any time point
 - Persistence of clinical symptoms of cUTI or new symptoms have developed
 - Initiation of rescue/non-study antibacterial drug therapy for cUTI
- **Indeterminate/Missing:** If the subject's outcome is neither clinical cure nor clinical failure, then the outcome should be listed as indeterminate/missing, including death where the cUTI is clearly noncontributory. If the Investigator did not complete an assessment or if the subject did not complete the study visit, the outcome is considered missing

Subjects who are assessed as a clinical failure at the EOT visit or beyond will have the failure carried forward to all subsequent visits.

Data for all subjects will be reviewed to ensure the Investigators are following the protocol defined criteria for clinical response and queries will be issued as needed to clarify any response that does not meet the protocol definition.

Microbiologic Response:

Per-subject microbiological response is defined as follows:

- **Microbiological success:**
 - Reduction of the baseline pathogen(s) to $<10^4$ CFU/mL
- **Microbiological failure:**
 - Blood cultures are positive for the baseline pathogen(s), or
 - Urine culture grows $\geq 10^4$ CFU/mL of the baseline pathogen(s)
- **Microbiological Indeterminate/Missing:** No interpretable urine culture data are available

The primary efficacy outcome is defined in [Table 5](#).

Table 5 Primary Efficacy Outcome

Primary Efficacy Outcome		
Clinical Response	Microbiological Response	Responder Outcome
Cure	Success	Responder
Cure	Failure	Non-responder
Cure	Indeterminate / Missing	Indeterminate
Failure	Success	Non-responder
Failure	Failure	Non-responder

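### SAP 3.1.6 lets some clinical failures leave the evaluable sets because of their outcome: the 3-day drug minimum has no failure exception, and the CE-TOC waiver stops at EOT

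*SAP*

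**What the plan says.** SAP 3.1.6 defines five CE sets (Day 5, EOI, EOT, TOC, FU). The rules that bear on failures are:

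- **Item 4 (study drug therapy), all five sets:** "The subject received at least 3 days of study drug". No carve-out for failures follows.
- **Item 3 (concomitant antibiotics):** a potentially effective non-study antibiotic excludes a subject, except one who is a clinical failure at the visit in question "and received non-study antibiotics for insufficient therapeutic effect of the study drug".
- **Item 5, CE-TOC:** "The TOC Visit occurred 13-18 days following randomization and at least 5 days following the last dose of study drug". The timing rule is lifted for failure at EOT, and the assessment rule likewise: "unless the patient was defined as a clinical failure at the EOT Visit".
- **Item 5, CE-FU:** the waiver is wider: "unless the patient was defined as a clinical failure at the EOT or TOC Visits".
- **SAP 3.1.7:** each ME set is a subset of micro-ITT and of the matching CE set. It adds: "Subjects who are microbiological failures prior to the TOC or FU Visit, and are otherwise evaluable, will be included in the ME-TOC and ME-FU populations", whatever the date of those visits.
- **SAP 5.7.1:** "Subjects who are assessed as a clinical failure at the EOT visit or beyond will have the failure carried forward to all subsequent visits".
- **SAP 1.2.3, Table 2, footnote 3:** "EOT assessments are to be performed at premature withdrawal or treatment failure and within 24-h of last dose".

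**The concern.** Protocol 9.4 has study drug stopped at treatment failure, so short exposure can be a consequence of failing. A minimum exposure is reasonable before crediting a drug with a cure. Applied to failures without exception, it makes membership of the analysis set depend on the outcome. The same holds where a failure counts only if the visit that recorded it fell inside a window.

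At stake is how far the CE and ME results can be trusted as a check on the main analysis. The protocol also makes ME at TOC one of two co-primary populations for the EMA. SAP 1.1.1 announces a separate EMA SAP, which is not among the documents. If it reuses these definitions, the gap enters a confirmatory non-inferiority test.

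**Working it through.** **1. Four cases traced through the rules**

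- *Fails and is rescued after two doses, failure recorded at EOT.* Carry-forward makes this a failure at TOC, so item 3 keeps the subject despite rescue, and item 5 waives the TOC assessment and window. SAP 5.6 counts expected doses over the days on drug, so compliance is 2/2 = 100% and the 80% rule is met. The 3-day minimum alone removes the subject from all CE sets and hence all ME sets.
- *Cured at EOT, recorded as a failure at a TOC visit on Day 11, no in-window TOC assessment.* (SAP 5.8.2 uses a Day 11 TOC visit as its own example of an out-of-window visit.) CE-TOC drops the subject. CE-FU waives its assessment and window rules for a failure at TOC, and 5.7.1 carries the failure forward. The same failure can count in CE-FU but not in CE-TOC.
- *Cured at EOT, relapses on Day 11, is rescued, and attends an in-window TOC visit as a failure.* Kept in CE-TOC.
- *Earlier microbiological failure, TOC visit out of window.* SAP 3.1.7 waives visit timing, but only for subjects otherwise evaluable and within an ME set that requires CE-TOC membership. The SAP does not say which rule prevails. Either way, the waiver does not lift the 3-day minimum.

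**2. The plan's own power figures**

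SAP Table 3 (10% margin), recomputed by Farrington-Manning:

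| Outcome | Total N | Stated | Recomputed |
|---|---|---|---|
| EOI, micro-ITT | 790 | >99% | 99.8% |
| TOC, micro-ITT | 790 | 80.0% | 80.1% |
| TOC, micro-MITT | 780 | 79.8% | 79.8% |
| TOC, ME | 720 | 84.7% | 81.1% |

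The ME figure does not reproduce at N = 720; 84.7% is what N = 780 gives. That is a separate matter, and power stays above 80%.

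**3. A plausible ceiling for the share of failures lost**

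From the planning rates in SAP 4.1:

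- micro-MITT non-successes: 780 × 0.21 = 163.8
- ME non-successes: 720 × 0.18 = 129.6
- share leaving between the two sets: (163.8 - 129.6) / 163.8 = 34.2 / 163.8 = 20.9%

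This includes indeterminates, which ME excludes by definition, so it is a generous upper value if the planning rates hold.

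**4. Effect on the difference**

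If a share f of failures is dropped from an arm with success rate p, the retained rate is p / (1 - f(1 - p)). Assume true rates of 69% (eravacycline) and 79% (ertapenem), exactly at the margin, with 390 per arm and one-sided alpha 0.005.

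For f = 5% in both arms: 0.69 / (1 - 0.05 × 0.31) = 0.7009 and 0.79 / (1 - 0.05 × 0.21) = 0.7984, a difference of -9.75 points. The last column is the chance that ME alone passes.

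| Lost, eravacycline / ertapenem | Difference (points) | ME passes |
|---|---|---|
| 0 / 0 | -10.00 | 0.50% |
| 5% / 5% | -9.75 | 0.63% |
| 10% / 10% | -9.49 | 0.80% |
| 15% / 15% | -9.20 | 1.03% |
| 20.9% / 20.9% | -8.85 | 1.41% |
| 15% / 5% | -7.47 | 3.95% |
| 5% / 15% | -11.48 | 0.11% |

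With true rates equal at 79%, losses of 15% / 5% give +1.73 points, and 5% / 15% give -1.73.

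**The case against.** The strongest reply is that no decision rule in this SAP is touched. The primary analysis is in micro-ITT, where windows are nominal (SAP Table 4) and indeterminate or missing outcomes stay in the denominator as failures (SAP 4.6). SAP 5.7.2 calls the CE and ME comparisons descriptive and rules out any non-inferiority conclusion from them. For the EMA, both micro-MITT and ME must pass (Protocol 15.2.1), and micro-MITT keeps every micro-ITT subject with at least one dose. In the illustration above, micro-MITT passes with probability 0.5%, so the joint claim cannot exceed that, whatever ME does. All of this stands and limits the impact.

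It can also be said that minimum exposure is a design choice, and that a carry-forward rule governs outcomes, not membership. That is fair: 5.7.1 does not strictly contradict item 5. But items 3 and 5 set out to keep failures in, and item 4 cancels that for the earliest ones. The unlike waivers for CE-TOC and CE-FU also have no stated reason.

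A reader might infer more than the text supports in three ways:

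- *That any relapse before Day 13 is dropped.* It is lost only if it was not a failure at EOT and no in-window TOC assessment follows. SAP Table 2 schedules no clinical outcome assessment between EOT and TOC, so the route is narrow. SAP 3.1.7 also has a timing waiver for earlier microbiological failures.
- *That the comparison is necessarily pushed toward no difference.* That follows if similar shares of failures are lost in both arms, not in general.
- *That a fixed part of the margin disappears.* Assuming 3% against 1% early failure and 90% cure in everyone else gives 0.97 × 0.90 - 0.99 × 0.90 = -1.8 points, all hidden after exclusion. But that assumption places the whole difference among the excluded subjects. It is also hard to square with the planned 93% EOI response: 3% would be 3/7, or about 43%, of all eravacycline non-response at EOI.

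**Conclusion.** The gap is real but modest. Early clinical failures leave all CE and ME sets through the 3-day minimum. A narrower group, failures first recorded at a too-early TOC visit with no in-window assessment, leaves CE-TOC. ME-TOC may be affected too, depending on how the 3.1.7 waiver is read.

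Attenuation is likely if losses are balanced: 0.25 to 1.15 points of a true -10 for 5% to 20.9% of failures lost. With unequal losses the bias can favour either arm. The shares lost and the true rates are assumptions; the documents give no early-failure or out-of-window rates, overall or by arm. The effect on ME may be smaller than on CE, because not every early clinical failure is a microbiological failure.

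The micro-ITT conclusion and micro-MITT are unaffected. The only confirmatory exposure is ME at TOC for the EMA, and only if the separate SAP adopts these definitions. This is an inexpensive improvement, not a threat to the trial's main conclusion.

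**What to change.** Before database lock:

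1. **SAP 3.1.6 item 4:** exempt Investigator-assessed clinical failures from the 3-day minimum, subject to a lower minimum exposure for failures that is fixed in advance. The exact value is open to debate; prespecifying it matters more.
2. **SAP 3.1.6 item 5, CE-TOC:** extend the waiver of the assessment and window rules to clinical failures recorded after EOT up to the end of the TOC window, in line with CE-FU and with the carry-forward in 5.7.1.
3. **SAP 3.1.7:** state how the waiver for earlier microbiological failures works with required CE-TOC membership.
4. **EMA SAP:** carry the same rules across.

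The cost is SAP wording and programming. The downside is that a few failures with little drug exposure enter CE and ME, so cure rates there fall slightly.

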3.1.7. Microbiologically Evaluable (ME) Populations

The ME-Day 5, ME-EOI, ME-EOT, ME-TOC and ME-FU populations will consist of all subjects in the micro-ITT and the CE-Day5, CE-EOI, CE-EOT, CE-TOC, CE-FU populations, respectively who also meet the following:

- Had a suitable urine specimen (as defined in [Section 3.1.4](#)) collected at the Day 5 (ME-Day 5), EOI (CE-EOI), EOT (ME-EOT), TOC (ME-TOC) and FU (ME-FU) Visits. Subjects who are microbiological failures prior to the TOC or FU Visit, and are otherwise evaluable, will be included in the ME-TOC and ME-FU populations regardless of when the TOC and FU visits occurred.
- The urine culture at the Day 5 (ME-Day 5), EOI (ME-EOI), EOT (ME-EOT), TOC (ME-TOC) and FU (ME-FU) Visits is interpretable with respect to determining microbiological outcome. An interpretable urine culture is one that has a clearly identified pathogen or one where the baseline pathogen(s) can be excluded. A urine culture will be considered uninterpretable if more than 2 bacterial isolates are identified unless the specimen is obtained via suprapubic aspiration, nephrostomy tube newly placed or cystoscopy, 1 of the isolates comprises $\geq 80\%$ of the total growth (predominant), 1 or more isolates are also isolated simultaneously from a blood culture, or there is $< 10^4$ CFU/mL (including no growth) of the baseline pathogen(s).

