 - If no interpretable post-baseline specimen is available, the microbiological response is considered indeterminate. By definition, subjects with an indeterminate response are included in the denominator for analyses in the micro-ITT and micro-MITT populations and thus, are considered failures. Subjects with an indeterminate response are excluded from the ME populations.
- Missing values for other individual data points will remain as missing. Missing values will not be imputed and only observed values will be used in data analyses and presentations.
- Where individual data points are missing, categorical data will be summarized based on reduced denominators (ie, only subjects with available data will be included in the denominators).

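### SAP 3.1.7 admits earlier microbiological failures to ME-TOC and ME-FU whatever the visit date, but the CE and ME windows exclude them and no rule scores them as failures

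*SAP*

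**What the plan says.** - **Membership, SAP 3.1.7.** ME-TOC and ME-FU are the micro-ITT subjects who are also in CE-TOC and CE-FU and who meet two culture criteria. The first criterion, a suitable urine specimen at the visit, carries a waiver: "Subjects who are microbiological failures prior to the TOC or FU Visit, and are otherwise evaluable, will be included in the ME-TOC and ME-FU populations". The waiver applies whatever the date of those visits. The second requires a culture at the visit that is "interpretable with respect to determining microbiological outcome", and it has no exception for earlier failures.
- **CE window, SAP 3.1.6, item 5.** CE-TOC requires that "The TOC Visit occurred 13-18 days following randomization and at least 5 days following the last dose of study drug", and exempts only subjects whom the investigator judged clinical failures at EOT. CE-FU requires days 20-29 and exempts only clinical failures at EOT or TOC.
- **Analysis window, SAP Table 4.** The CE and ME columns repeat days 13-18 (and at least 5 days after last dose) for TOC and days 20-29 for FU, with no exception.
- **Scoring, SAP 5.7.1.** Microbiological success is "Reduction of the baseline pathogen(s) to $<10^4$ CFU/mL". Failure is growth at or above that level, or a positive blood culture for the baseline pathogen. The only carry-forward rule is clinical: "Subjects who are assessed as a clinical failure at the EOT visit or beyond will have the failure carried forward to all subsequent visits".
- **Indeterminates, SAP 4.6.** "Subjects with an indeterminate response are excluded from the ME populations".
- **Use.** SAP 5.7.2 summarizes microbiological response by visit in ME, for description only. Protocol 15.2.1 makes microbiological success at TOC in ME one of two EMA co-primary measures. SAP 1.1.1 leaves the EMA analysis to a separate SAP.

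**The concern.** For clinical failure the SAP has a matched pair of rules. A clinical failure at EOT is excused from the TOC assessment and window, and is then scored as a failure at TOC. For microbiological failure only the first half exists. The evident purpose of the waiver is that a known failure should not leave the analysis because a later visit was mistimed. Yet the rules it depends on still remove the subject, and if the subject stays, the mistimed culture may set the result.

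ME is the population meant to be sensitive to a treatment difference. Dropping known failures, or turning them into successes through late cultures, raises its success rates. If this happens more often in one arm, it biases the difference. SAP 3.2.2 says ME inclusion is determined programmatically, so two programmers following the text could produce different denominators and different numerators.

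**Working it through.** **1. The plan's own ME figure.** SAP Table 3 gives 84.7% power for ME-TOC with 720 subjects (360 per arm), 82% in both arms, margin 10% and one-sided alpha 0.005. Farrington-Manning power is Φ{[(p1 − p2 + 0.10) − z·s0]/s1}. Here z = 2.576, s1 = √(2 × 0.82 × 0.18/360) = 0.02864, and s0 = 0.02902 from the restricted estimates 0.760 and 0.860. This gives (0.10 − 2.576 × 0.02902)/0.02864 = 0.882, or 81.1%. The stated 84.7% is what 780 subjects would give. The other three rows of the table reproduce. This is a separate discrepancy, and the present point does not rest on it.

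**2. The rules applied to records.** Every record is in micro-ITT and otherwise evaluable. All but the last grew 10^5 CFU/mL of the baseline pathogen at EOT.

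| Record | 3.1.7 waiver | CE-TOC window | TOC score under 5.7.1 if retained and the culture is used |
|---|---|---|---|
| A. Clinical cure at EOT; TOC culture day 19, <10^4 | in | out | success |
| B. As A, but day-19 culture ≥10^4 | in | out | failure |
| C. Clinical failure at EOT, rescued; TOC culture day 19, <10^4 | in | exempt | success |
| D. Clinical cure at EOT; no TOC visit | not covered | out | none |
| E. Clinical cure at EOT; TOC culture day 17, <10^4 | not needed | in | success |
| F. No earlier failure, clinical cure; TOC culture day 19, <10^4 | not covered | out | none |

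- A shows the conflict. Section 3.1.7 both includes the subject by the waiver and excludes the subject by nesting in CE-TOC. If the waiver wins, a culture that keeps F out of the set makes A a success.
- C shows that the scoring gap remains where membership is not in dispute. SAP 3.1.6, item 3 lets a rescued clinical failure stay evaluable. A late negative culture, possibly the effect of rescue, then meets the success definition. If Table 4 removes that culture, the subject has no TOC result in a set that admits no indeterminates.
- E lies outside the waiver but raises the same unanswered question: does an EOT microbiological failure with a later in-window negative culture count as a success?

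**3. Search for a scoring rule elsewhere.** Protocol 14.2.3 takes the worst outcome across pathogens, not across visits. Protocol 15.2.1 and SAP 5.7.2 score by visit. SAP 4.6 deals with missing cultures. None of them carries a microbiological failure forward.

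**4. Size.** The documents give no rate of EOT microbiological failure or of mistimed TOC cultures, so these inputs are assumptions.

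- EOT failures 3-6% of 720: 22 to 43 subjects.
- Share of those with an out-of-window TOC culture 5-20%: 22 × 0.05 = 1.1 to 43 × 0.20 = 8.6, so about 1 to 9 subjects. The middle of both ranges, 32 × 0.125, gives 4.
- One subject is 1/360 = 0.28 points in an arm. Four are 4/720 = 0.6 points on the pooled rate. Nine are 9/720 = 1.25 points pooled, or 9/360 = 2.5 points on the difference if all fall in one arm.

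These are upper figures, because they assume that every late culture is negative.

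**5. Effect on the EMA test.** Take true rates at the margin, 72% versus 82%. If equal shares of each arm turn from failure to success, the chance of declaring non-inferiority stays at 0.5%. With 3 eravacycline and 1 ertapenem subjects (72.83% versus 82.28%) the formula in step 1 gives 0.8%. With 2% versus 1% of each arm (about 7 and 4 subjects, beyond the range above) it gives 1.2%.

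**The case against.** The best defense reads 3.1.7 as strictly nested. The phrase "and are otherwise evaluable, will be included in the ME-TOC and ME-FU populations" would then mean that the subject must first pass every CE-TOC rule, including its window. Record A is simply out, and no late culture creates a success. The waiver would serve EOT clinical failures, whom 3.1.6 already excuses. This reading is possible, but it leaves the waiver almost nothing to do for visit timing, and it drops known failures such as A. It does not settle how C is scored.

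Three parts of the defense stand:

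- A reader might infer that every retained earlier failure becomes a success or an indeterminate. That is not so. If record B is retained, it is a failure under 5.7.1 with or without a carry-forward rule.
- A reader might infer that subjects with no TOC visit enter ME as indeterminates. The waiver covers timing only, and record D fails the interpretable-culture criterion, so D stays out.
- The Microbiological Outcomes Review Plan cited in SAP 3.2.1 and the EMA SAP are not among the documents, and either could hold a scoring rule.

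**Conclusion.** The point holds as a conflict between stated rules together with a missing scoring rule. A known EOT microbiological failure with an out-of-window TOC culture below 10^4 CFU/mL can be dropped, or be counted as a TOC success from a culture that would exclude a subject with no earlier failure.

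The effect is probably a few subjects. The range of 1 to 9 rests wholly on the assumed shares. The 93-94% EOI responder rates in the sample-size section do not bound it, since they concern a different endpoint, visit and population. Bias in the difference also requires imbalance between arms.

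A reader might go further and conclude that the main non-inferiority result is at risk. The documents do not support that. The FDA primary analysis uses micro-ITT with nominal visits, and ME microbiological results in this SAP are descriptive. The weight falls on the EMA co-primary ME analysis if these definitions are carried into its SAP. The correction should be made before database lock, but it is not a reason to doubt the primary analysis.

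**What to change.** 1. In SAP 3.1.6, 3.1.7 and Table 4, state that the timing waiver for earlier microbiological failures overrides the CE-TOC and CE-FU visit windows for the purpose of ME membership.
2. In SAP 5.7.1, state that a subject retained under this waiver, with microbiological failure at EOT (or at TOC, for FU), is scored a microbiological failure at the later visit, and that the out-of-window culture is not used. Starting at EOT matches the clinical carry-forward. It also avoids carrying forward a Day 5 failure that had cleared by EOT, which a rule covering any earlier visit would do.
3. State how an in-window negative culture after an EOT failure is scored, including one taken after rescue antibiotics. Without this, a day-18 and a day-19 culture in otherwise identical subjects would be handled differently with no stated reason.
4. Use the same text in the EMA SAP.

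The cost is a few sentences and a few lines of derivation code before database lock. ME success rates may be slightly lower.
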